6.4 Patient Registration and Numbering

Each enrolled patient will be assigned a composite number consisting of the three letter abbreviation for the study, a single digit for the center, a 3 digit number representing the next higher number serially from 1 – 90 followed by a single letter representing the arm to which the patient was randomized e.g. “PEC/1/001/C” meaning Pasireotide, Everolimus or combination study, Emory center, patient number 1, randomized to the combination arm.

Eligible patients will be entered on study centrally at the Emory University Winship Cancer Institute by the Study Coordinator. To verify slot availability, all sites should call the Study Coordinator:

[name], CCRC

[contact]

[contact]

[name]

Email: [contact]

Before an investigator may enroll patients, a signed IRB approval letter and approved consent form must be on file with the coordinating center at Emory WINSHIP CANCER INSTITUTE.

Prior to discussing protocol entry with a patient, call or e-mail to verify slot availability.

Once it is confirmed that a slot is available, call and fax a completed eligibility checklist, required laboratory tests and signed consent form to the coordinator at [contact]) between 9 a.m. and 4 p.m. ET, Monday through Friday.

At the time of registration, WINSHIP CANCER INSTITUTE coordinating center will verify the following:

- IRB approval at the registering institution
- Patient eligibility
- Existence of a signed consent form
- Existence of a signed authorization for use and disclosure of protected health information.
- Patient consent for tumor biopsy or special studies (if applicable)

After verifying eligibility, the Emory WINSHIP CANCER INSTITUTE Clinical Research Coordinator will contact the study statistician, [name], PhD; (Research Assistant Professor, Department of Biostatistics and Bioinformatics, Rollins School of Public Health & Biostatistics Shared Core Resource; [name]; [contact]; [contact]. Email: [contact]) to randomize patient, assign a study number and a dose. The coordinator is expected to fax a confirmation back to the registering site within 24 hours.

Treatment on this protocol cannot begin prior to registration and must be administered at each site under the supervision of a medical oncologist.

All screening procedures should be completed within 14 days prior to treatment unless otherwise specified in the Study Calendar or specific sections of this protocol. Issues that would cause treatment delays should be discussed with the Principal Investigator. If a patient does not receive protocol therapy following registration, the patient's registration on the study may be canceled. The Study Coordinator and or the study PI should be notified of cancellations as soon as possible.

Investigational agents may be ordered by a participating site only after the initial IRB approval for the site has been forwarded to the study regulatory specialist at the Emory University WINSHIP CANCER INSTITUTE.

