In some circumstances it may be difficult to distinguish residual disease from normal tissue. When the evaluation of complete response depends on this determination, it is recommended that the residual lesion be investigated (fine needle aspirate/biopsy) to confirm the complete response status.

Confirmation

The main goal of confirmation of objective response is to avoid overestimating the response rate observed. In cases where confirmation of response is not feasible, it should be made clear when reporting the outcome of such studies that the responses are not confirmed.

To be assigned a status of PR or CR, changes in tumor measurements must be confirmed by repeat assessments that should be performed no less than 4 weeks after the criteria for response are first met. Longer intervals as determined by the study protocol may also be appropriate.

In the case of SD, follow-up measurements must have met the SD criteria at least once after study entry at a minimum interval (in general, not less than 6-8 weeks) that is defined in the study protocol

Duration of Overall Response

The duration of overall response is measured from the time measurement criteria are met for CR or PR (whichever status is recorded first) until the first date that recurrence or PD is objectively documented, taking as reference for PD the smallest measurements recorded since the treatment started.

Duration of Stable Disease

SD is measured from the start of the treatment until the criteria for disease progression are met, taking as reference the smallest measurements recorded since the treatment started.

Response Review

For trials where the response rate is the primary endpoint it is strongly recommended that all responses be reviewed by an expert(s) independent of the study at the study’s completion. Simultaneous review of the patients’ files and radiological images is the best approach. A central review of all responses is planned for the end of the study. Nonetheless, decision regarding treatment continuation will be based on the treating physician’s assessment with the concurrence of the PI in cases where there is differences of opinion.

Reporting of Results

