7.7 Exploratory biomarker assessments

7.7.1 Sample collection

Refer appendix B for details of sample collection, handling, preservation and shipping

Blood Sample Collection:

Blood samples will be collected at the indicated times into heparinized green top tubes (7 mls for PBMC collection - optional), red top tube (7 mls to obtain serum sample for ELISA assay). PBMC will be purified using standard Ficoll-Paque gradient centrifugation according to the instructions of the manufacturer (Amersham Pharmacia, Uppsala, Sweden). All samples must be stored away within 2 hours of collection by refrigeration at -70 to -80°C until ready for assay.

Paraffin-Embedded Tissue

Archival paraffin embedded tissue collected at the time of patient screening will be shipped to the lab of [name] at the Winship Cancer Institute. If the entire paraffin block cannot be submitted, 15-20 slides of 4-5 micron sections cut from the block should be submitted. The patient ID # should be provided with the specimens.

ELISA Assay

ELISA detection and quantification of the cytokines of interest will be performed using previously published methods. Samples will be loaded onto a 96-well microtiter plate coated with monoclonal antibody specific for the cytokine of interest. After a blocking step, samples will be diluted into a buffer and incubated with the primary antibody. After a washing step, antisera specific for the cytokine is added followed by additional incubation. Another washing step will be performed to be followed by the addition of peroxidase-conjugated secondary antibody. The concentrations of the respective cytokines will be determined in triplicate for each serum samples using an ELISA plate reader. A set of calibrators and assay controls will be run with each assay.

Immunohistochemistry (IHC) for mTOR pathway proteins and somatostatin receptor expression

Immunohistochemical detection of the mTOR pathway proteins will be carried out with the avidin-biotin technique using specific monoclonal antibodies targeting the proteins of interest. The IHC will be performed in collaboration with, [name] and on a fee-for-service basis using the personnel and resources provided by the Pathology Core facility at Emory Winship Cancer Institute. Semiquantitative scoring of protein expression will be performed by [name] (prior pathology training) in collaboration with [name] a staff anatomic pathologist with Emory University Hospital.

8 Data Review and Data Management

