8.1 Data Monitoring Committee

The institution data safety monitoring committee will review the outcome of the study at regular intervals as mandated by institutional policy or more frequently if deemed necessary by the Principal Investigator. The Data Monitoring Committee (DMC) will be composed of medical, ethics and statistical experts and will meet to review the efficacy and safety data and determine a risk/benefit analysis in this subject population. The purpose of the DMC is to advise on serious safety considerations, lack of efficacy and any other considerations within the charge to the Committee. The DMC may request additional meetings or safety reports as deemed necessary upon discussion with Novartis and its representatives. The DMC may stop the study following review of results from each interim analysis. Appropriate efficacy and safety data summaries will be provided to the DMC after each interim analysis.

In addition, the principal investigator will review the toxicities as they occur and/or are reported. The approval of the principal investigator or designee is necessary for accrual of all patients.

The Data Coordinating Center will review responses and toxicity and report these to the regularly scheduled meetings of the Data Safety Monitoring Committee of the Emory Winship Cancer Institute

Each participating site is expected to have its own data monitoring and safety plan (DMSP) with regard to forwarding information to their IRBs. If the data reveals a change in the risk/benefit ratio, the investigator will notify the IRB and the PI. The principal investigator and co-investigators will review the data and forward any changes or protocol amendments to the IRBs. All serious adverse events will be reported promptly or periodically to the IRB according to the requirements specified in the IRB policy and guidelines. All study participant information will be kept in a confidential manner by the assigning of a random number to each study participant. All data will be kept confidential as per institutional guidelines and policies. Any breach of confidentiality is a serious matter and conflicts with institutional policies and will be reported to the IRB. A cumulative summary of all adverse events occurring on this study and a report of the

data safety and monitoring plan will be submitted to the IRBs with the annual renewal reports. Enter information concerning the data monitoring board

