9.2 CBR as endpoints

Any treatment arm that was closed to accrual after the first stage analysis will be considered to be an inferior arm. The CBR rates of all arms with complete accrual of 28 evaluable patients will be estimated and used as additional reference for the determination of the winner arm to be considered for further study.

9.3 Other Endpoints:

Preclinical evidence show that mTOR inhibitor resistance may be due to increased survival pathway signaling activity with resultant addiction of the tumor cells to this pathway. The trial will explore the potential benefit of sequential versus concurrent initiation of mTOR inhibitor and Pasireotide. For this purpose, patients randomized to the single agent arms will be allowed to receive the 2-drug combination at the time of disease progression. Such patients may, however, remain on treatment only if they achieve disease stabilization or objective response at the end of

the first 2 cycles of 2-drug combination using the last imaging scan obtained while on the single agent therapy as the new baseline.

9.4 Correlative Study Analyses:

The expression of somatostatin receptor and mTOR pathway protein (S6, pS6, 4E-BP1, p-4E-BP1, eIF4e, Akt, pAkt, raptor, rictor, PRAS40, mSin1, FKBP38, IGF-R, IRS-1 and HIF1- α) in archival tissue and in fresh tumor biopsy obtained at the time of progression will be determined by immunohistochemistry and quantified by immunoscore as previously described.⁵² Differences in mean expression between the 3 treatment arms will be compared with ANOVA or Chi-Square test. Longitudinal analyses will also be conducted to investigate the association between the treatment arm and changes in circulating IGF-1 using ELISA assay and immunoscore of the listed proteins in progressing patients. The MIXED procedure of SAS will be used for the analyses.

10 Protocol amendments, or changes in study conduct

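### The patient ID carries the randomized arm and goes with the tissue, so IHC can be scored with the arm visible; separately, no masking is stated for the central response review

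*Combined protocol and SAP*

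**What the plan says.** Section 6.4 gives every enrolled patient a composite number: study abbreviation, center digit, serial number from 1 to 90, "followed by a single letter representing the arm to which the patient was randomized". Its worked example ends in C, for the combination arm.

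Section 7.7.1, under the paraffin-embedded tissue heading, states: "The patient ID # should be provided with the specimens". The IHC paragraph of the same section continues: "Semiquantitative scoring of protein expression will be performed by" readers at the coordinating institution. It does not say whether they know the arm.

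Section 9.4 uses the scores in two ways. It says "Differences in mean expression between the 3 treatment arms will be compared with ANOVA or Chi-Square test", and it plans longitudinal models relating treatment arm to changes in immunoscore in progressing patients. The material is archival tissue and tissue "in fresh tumor biopsy obtained at the time of progression". The introduction to Section 9 adds an analysis of whether a marker's effect differs by arm.

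Section 8.1 says that participant information will be "kept in a confidential manner by the assigning of a random number to each study participant".

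On response, Section 7.4 states: "A central review of all responses is planned for the end of the study". It recommends experts independent of the study and describes reading patient files and images together as the best approach. It does not mention masking or image labels.

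Section 6.6 says the trial is unblinded and names the investigator and the patient as those who know the assignment.

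**The concern.** A semiquantitative IHC score is a reader's judgment. If the label shows the arm, expectations about everolimus, pasireotide or their combination can shift the score. Any such shift falls on the contrast that Section 9.4 analyzes. In an open-label trial the sites cannot be masked, but a laboratory reader can be, with little effort. The plan does not take that opportunity, and its ID format works against it.

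The central response review raises a related question by a different route. Response rate is a primary endpoint, and it determines both whether an arm passes and which arm is chosen. An independent read gives most protection when the reader does not know the treatment, and the plan does not say whether that is so.

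**Working it through.** No arithmetic applies. The plan states no figure on masking or reader error, so the check sets the provisions side by side.

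**IHC scoring**

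1. *What does the ID contain?* Section 6.4: the randomized arm, as the last character.
2. *Is there another identifier that the laboratory could use?* Section 6.4 constructs only this one. The protocol defines no screening number or specimen code. Section 8.1 mentions a random number but does not say how it is generated, where it is used, or how it relates to the serial ID.
3. *Does the ID reach the laboratory?* Section 7.7.1: yes, it is to accompany the tissue.
4. *Is the readout open to judgment?* Section 7.7.1: yes, scoring is semiquantitative.
5. *Is any recoding or masking stated?* None was found in Sections 6.4, 6.6, 7.7, 9.4 or Appendix B.
6. *Does the arm enter the analysis of the score?* Section 9.4: yes, in the three-arm comparison and in the longitudinal models.

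Steps 1 to 6 together mean that a laboratory following the plan can score with the grouping variable in view. The exposure differs by sample:

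- Archival tissue: "Archival paraffin embedded tissue collected at the time of patient screening" predates randomization, so the arm letter does not exist at collection. It does exist once the full ID is attached. Which label is used at shipping is not stated.
- Progression biopsies: the arm was assigned long before, so the full ID is available. These samples feed the change-over-time models, where treatment arm is the explanatory variable. They are the more exposed set.

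**Identifier**

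Section 6.4 describes a serial number plus an arm letter, and Section 8.1 describes a random number. The Section 6.4 ID is not random. Either a second identifier exists and is undefined, or one of the two statements is wrong.

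**Central response review**

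1. The sentence that sends the ID with specimens is under the tissue heading. It does not mention scans.
2. Section 7.4 neither masks nor unmasks the reviewers.
3. Section 7.4 favors files read together with images. In an open-label trial such files would ordinarily show the treatment. This is an inference, not a statement in the plan.

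The supportable conclusion for this part is that masking is unspecified and that the favored method makes knowledge of the arm likely.

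**The case against.** **The IHC work is exploratory.** This stands. Section 3.3 lists it under exploratory objectives, and Section 9 gives no power calculation for it. The progression samples come from a limited number of patients on the single-agent arms. IHC plays no part in the response rule that decides whether an arm passes. All this limits the importance of the point but does not remove it.

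**Archival tissue predates the arm letter, and the ID shows arm, not response.** Both are true. The label on archival tissue is therefore uncertain, and correlations of marker with response within one arm are less exposed. The between-arm comparisons and the progression biopsies remain exposed.

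**The trial is open-label.** Section 6.6 names only the investigator and the patient. Nothing requires scorers or central reviewers to know the arm.

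**The random-number sentence is only about confidentiality.** It is, and reconciling it is a wording correction. It still leaves the identifier ambiguous.

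**A stronger reading is tempting.** A reader might infer that the same ID unmasks the response review, so that one biased read could flip an arm at the threshold of 3 responses in 28. The documents do not support this. They do not say that scans carry the ID. They do not say that the central read replaces the site's call in the decision rule. A review of all responses may only re-read responses already called, in which case it could remove a response but not add one. How often an arm lands near the threshold also says nothing about bias, because it is the same with or without masking. Nor would relabeling alone mask a review that includes patient files.

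**Conclusion.** The point holds in two parts of different strength.

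- *IHC scoring.* As written, the ID format and the specimen instruction allow scorers to see the arm, on scores that are then compared by arm. This follows from the text, on the assumption that the ID in Section 7.7.1 is the one defined in Section 6.4, the only patient ID the protocol constructs. The identifier statements in Sections 6.4 and 8.1 conflict and need to be reconciled.
- *Central response review.* Masking is not specified, and the favored method of reading files with images would probably disclose treatment. This is a gap to close. It does not show that the review is unmasked.

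The size cannot be stated as a number: the documents give no reader error rate and no basis for deriving one. No sample size, power or error rate changes. The change is worth making because it is cheap and removes an avoidable source of bias, but the IHC part affects exploratory results only.

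**What to change.** 1. Section 6.4: remove the arm letter from the patient ID and hold the arm in a separate database field.
2. Sections 6.4 and 8.1: describe one identifier scheme. If a random number is intended, say that it is the arm-free code and where it is used.
3. Section 7.7: label all tissue, archival and progression, with the arm-free code. State that IHC scorers are masked to arm and to outcome.
4. Section 7.4: state that central response reviewers read images under an arm-free code, with treatment information withheld from any accompanying files.

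The cost is a change of numbering convention, some relabeling, and a modest amount of redaction where files accompany images. Treatment, visits and sample size are untouched.

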6.6 Treatment blinding

This is an unblinded randomized trial. Both the investigator and the patient will be aware of treatment assignment at the time of enrolment.

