7.4 Efficacy

Primary efficacy assessment

The primary endpoints of this study are response rate (RR) and progression free survival (PFS). Interim analysis for the RR primary endpoint will be performed after 18 evaluable patients have been enrolled for each arm of treatment. Any arm not meeting the pre-specified efficacy RR (specified in Section 10.1 under statistical analysis) will be closed to further accrual. Tumor response assessment will be performed after every two cycles of therapy using cross-sectional imaging according to the RECIST 1.1 criteria.

All patients who completed at least 2 cycles of therapy will be deemed evaluable for the efficacy endpoint. In the event of study discontinuation prior to completing two treatment cycles for reasons other than disease progression, the affected subject will be considered inevaluable for efficacy and will be replaced by another subject (comparable as per stratification criteria) to be enrolled on the same arm of the study.

Patients who discontinue treatment due to drug-related toxicity prior to obtaining a restaging scan would be considered inevaluable and would be replaced.

Patients who discontinue treatment for symptomatic disease progression prior to a restaging scan would be deemed to have progressed as of the time of treatment discontinuation and will not be replaced.

Patients who are lost to follow-up will be censored as of the last official contact date for efficacy and survival outcome analysis. If the event occurred prior to the first restaging scan such patients will be deemed inevaluable for RR efficacy endpoint and will therefore be replaced by another

patient. They will, however, remain evaluable for overall safety assessment provided they have received at least one dose of the study drug..

Secondary efficacy assessments

Assessment for other secondary and exploratory endpoint will be performed at study conclusion.

Patient will be evaluable for overall toxicity and safety endpoint determination if they received any dose of the investigational agent.

Any patient deemed inevaluable for efficacy assessment as a result of treatment discontinuation due to treatment-related toxicity may still be evaluated for overall safety profile assessment.

Notwithstanding this provision, however, only patients who are evaluable for the primary efficacy endpoint may be included in the safety assessment conducted for the sole of picking a winning arm for the trial.

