All patients included in the study must be assessed for response to treatment, even if there are major protocol treatment deviations or if they are ineligible. Each patient will be assigned one of the following categories: 1) complete response, 2) partial response, 3) stable disease, 4) progressive disease, 5) early death from malignant disease, 6) early death from toxicity, 7) early death because of other cause, or 9) unknown (not assessable, insufficient data).

All of the patients who met the eligibility criteria should be included in the main analysis of the response rate. Patients in response categories 4-9 should be considered as failing to respond to treatment (disease progression). Thus, an incorrect treatment schedule or drug administration does not result in exclusion from the analysis of the response rate. Precise definitions for categories 4-9 will be protocol specific.

All conclusions should be based on all eligible patients.

Subanalyses may then be performed on the basis of a subset of patients, excluding those for whom major protocol deviations have been identified (e.g., early death due to other reasons, early discontinuation of treatment, major protocol violations, etc.). However, these subanalyses may not serve as the basis for drawing conclusions concerning treatment efficacy, and the reasons for excluding patients from the analysis should be clearly reported.

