- ii. Documentation of the qualifications, training and experience of the PI and other study staff
- iii. Eligibility of consented/enrolled patients
- iv. Informed consent document and process
- v. Verification that the local PI and staff are performing trial functions in accordance with protocol
- vi. Accuracy, completeness and timeliness of data
- vii. Accuracy and completeness of all source documentation
- viii. Response evaluation: verify that responses are identified according to the protocol definition of response for any response that is a major endpoint
- ix. Toxicity
- x. Appropriate reporting of all AEs and SAEs as required by GCP, the protocol, IRB regulations, sponsor's SOPs and other regulatory requirements

The monitor shall meet with RN/Coordinator assigned to the trial to:

provide an itemized review of the deficiencies to the RN/Coordinator and remove items from itemized review which are corrected during this meeting

review and document corrections; the RN/coordinator should indicate any remaining deficiencies and provide corrective action plan for resolution

prepare summary report for PI and Monitoring Committee to include summary of systematic deficiencies, significant protocol deviations, summary of remaining deficiencies and RN/coordinator corrective action plan, recommendations for data collection, protocol revision for clarity

The Monitor shall meet with the overall PI to discuss the report and document the PI's responses prior to submitting final report to the Monitoring Committee

The final Monitoring Committee review of audit report and PI response and PI summary of protocol to date will be included in the annual renewal submission.

Egregious data insufficiencies that may impact the scientific integrity of the trial are reported to the Medical Director and Clinical Trial Review Committee.

Please see the attached supplementary Emory University WINSHIP CANCER INSTITUTE data safety monitoring plan policy document for a complete detail of the monitoring plan.

9 Statistical methods and data analysis

All treated subjects will be included in the analysis of efficacy and safety.

Demographic and baseline characteristics will be summarized using descriptive statistics. The toxicities will be tabulated by organ system. Time to disease progression and overall survival will be evaluated using the Kaplan-Meier method.

Correlative analysis will be exploratory in the context of this Phase II screening trial.

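### Section 6.4 lets a randomised but untreated patient's registration be cancelled once the open-label arm is known, and nothing requires such patients to be analysed or reported by arm

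*Combined protocol and SAP*

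**What the plan says.** Section 6.4 sets the order of events. Once eligibility is verified, the coordinator contacts the study statistician "to randomize patient, assign a study number and a dose". The number is serial, from 1 to 90, "followed by a single letter representing the arm to which the patient was randomized". Then: "The coordinator is expected to fax a confirmation back to the registering site within 24 hours". Treatment may not start before registration. Section 6.6 adds: "Both the investigator and the patient will be aware of treatment assignment at the time of enrolment".

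Section 6.4 goes on to say that, for a patient who gets no protocol therapy after registration, the "registration on the study may be canceled". The next sentence asks that the study coordinator and/or the principal investigator be told of cancellations as soon as possible. It names no criteria and no decision-maker, and it does not ask for the arm or the reason to be recorded.

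On who is analysed, section 7.4 (Reporting of Results) states: "All conclusions should be based on all eligible patients". The opening of section 9 states: "All treated subjects will be included in the analysis of efficacy and safety". Section 7.4 also says that a patient who stops before two cycles for reasons other than progression "will be considered inevaluable for efficacy and will be replaced by another subject" on the same arm. Section 9.1 names the arm with the best response rate as the winner, provided it has at least 3 responses.

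**The concern.** The cancellation rule applies in the interval between an unblinded randomisation and the first dose. The arms ask different things of the patient: a daily tablet, an injection every four weeks, or both. It is plausible that some patients or investigators would go ahead on one arm and not on another. If those who drop out at this point differ in prognosis from those who stay, the groups being ranked are no longer the groups that randomisation formed.

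The study calls itself non-comparative, but sections 4 and 9.1 still rank the arms to pick a winner. About 4 responses per arm are expected at the design rate (28 × 0.15 = 4.2), so losing a few patients selectively can change the order. The same selection would affect each arm's test against 5%.

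The plan offers no way to judge afterwards whether this happened. Section 7.1 requires data on screening failures, meaning patients found ineligible. A cancelled patient was eligible, so that rule does not apply.

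**Working it through.** **1. The plan's own figures.** Inputs from Figure 4-1: null rate 5%, target rate 15%, alpha 0.20, power 80%; stop at 0 of 18; reject at 2 or fewer of 28. For a response rate p, the probability of a positive result is the sum, over x = 1 to 18, of P(Bin(18, p) = x) × P(Bin(10, p) ≥ max(0, 3 − x)).
- p = 0.05: 0.158, within the 0.20 limit.
- p = 0.15: 0.803, matching the stated 80%.
- Enrolment: section 7.4 expects about 5% inevaluable; 28 / 0.95 = 29.5, rounded up to 30 per arm and 90 in total, as in section 5.

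The design figures reproduce. The point concerns procedure and does not rest on an error in them.

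**2. Where a cancelled patient falls.**

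| Rule | Patient set | Randomised, eligible, never treated |
|---|---|---|
| 7.4, Reporting of Results | all eligible | counted, as a non-responder, unless cancellation is taken to remove the patient from the study |
| 9, opening | all treated | not counted |
| 7.4, evaluability | completed two cycles, or progressed earlier | not counted, on the natural reading |
| 7.1 | screening failures | not covered |

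The documents do not say which of these governs a cancelled registration.

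**3. Possible effect on the ranking.** The documents give no cancellation rate, so this is an illustration. Assumptions: two arms, each with a true response rate of 15%; 28 evaluable patients per arm; stage 1 stopping ignored; a share c cancelled in one arm only; every cancelled patient a would-be non-responder (the worst case). The response rate among the remaining patients in that arm is then 0.15 / (1 − c). With X ~ Bin(28, 0.15/(1 − c)) for that arm and Y ~ Bin(28, 0.15) for the other:

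| c | Rate in affected arm | P(X > Y) | Tie | P(X < Y) |
|---|---|---|---|---|
| 0 | 15.0% | 42.5% | 15.0% | 42.5% |
| 2% | 15.3% | 43.8% | 14.9% | 41.3% |
| 5% | 15.8% | 45.8% | 14.8% | 39.4% |
| 10% | 16.7% | 49.5% | 14.5% | 36.1% |

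The 5% row treats the plan's whole allowance for inevaluable patients as cancellations in one arm. If cancellation is unrelated to prognosis, the remaining patients still respond at 15% and the first row applies whatever c is.

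**4. What an all-randomised check does.** With untreated patients counted as non-responders, the expected rate in the affected arm is (1 − c) × 0.15 / (1 − c) = 15%. In this illustration the check therefore removes the shift in expectation. The ranking on evaluable patients does not change.

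**The case against.** The strongest reply is that cancellation does little that the analysis sets do not already do. A never-treated patient is outside the treated set of section 9 and, on the natural reading, outside the evaluable set of section 7.4, whether or not the registration is cancelled. Forbidding cancellation would leave the evaluable-patient ranking as it is. This stands, and it limits the claim: the gain lies in a complete record and a check, not in a corrected primary ranking.

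A reader might infer that cancelled patients vanish without trace. The documents do not support that. Cancellations are to be notified, registration is central, the serial number carries the arm letter, section 8.3 has the eligibility of consented and enrolled patients audited, and section 11.5 requires records to be kept. No text says that a patient is deleted, that a number is reissued, or that a cancelled patient leaves the eligible set. What is missing is an instruction to keep these patients in an analysis and report them by arm.

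A reader might also infer that the protocol permits cancellation because of the assigned arm. It does not name assignment as a reason; it only fails to exclude it. Nor does section 6.4 flatly contradict the all-eligible rule, since a cancelled patient could still be counted there in the not-assessable category. The conflict that is plain on the page is between that rule and the treated-subjects rule of section 9.

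Finally, the 10% row above is extreme: one arm only, and all non-responders. It should not be read as a likely size.

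**Conclusion.** The point holds as a gap in procedure. Section 6.4 allows removal after randomisation with the arm known, and the plan neither assigns such patients to an analysis set nor requires them to be reported by arm. Sections 7.4 and 9 disagree on whether they count.

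The size of any bias in the choice of winner is unknown. Under the one-sided worst case at 5%, the ranking of two equally active arms shifts from 42.5% each to 45.8% v 39.4%; without a link to prognosis the shift is zero. These figures rest on the assumptions listed with them, not on any rate in the documents. The sample size and the two-stage rule are unaffected. This is a cheap improvement, not a defect that undermines the design.

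**What to change.** - **Section 6.4:** replace the cancellation sentence. Once a patient is randomised, the registration is not cancelled and the patient keeps the number and arm. Untreated patients are reported by arm with the reason.
- **Replacement:** state that such a patient may be replaced for the 18 and 28 evaluable counts under the section 7.4 rule, with the replacement given a new number.
- **Section 9.1:** prespecify a repeat of the response-rate ranking with all eligible randomised patients in the denominator and untreated patients counted as non-responders, consistent with Reporting of Results in section 7.4. Present it as a check on the winner. The evaluable-patient rule stays as it is.
- **Sections 7.4 and 9:** reconcile the all-eligible and all-treated statements, so that the status of a randomised, untreated patient is explicit.

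The cost is a few sentences, one line in the patient flow and one more table. The response rate in the check will be slightly lower, and numbering may run past 90 if patients are replaced.
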